10.1 Name, description and source of each IMP and placebo

Metformin 500 mg capsules will be sourced from TEVA UK Ltd and supplied to Bilcare GCS (Europe) LTD (MIA IMP license number 10284).

Bilcare will over-encapsulate metformin 500 mg capsules and provide matched placebo capsules. The resulting metformin 500 mg capsule will appear identical in weight, colour and size to the placebo capsules

Metformin/placebo 500 mg capsules will be packaged into containers to hold sufficient doses for the patient to complete 35 days of prescribed treatment according to the research protocol.

The product labels will be fully compliant with both Annexe 13 of the Rules and Guidance for Pharmaceutical Manufacturers and Distributors (Orange Guide) and the protocol.

Metformin capsules and matched placebo will be stored at ambient room temperature until the expiration/retest date allocated by Bilcare.

10.2 Accountability procedures for the investigation product, including the placebo

The study treatment will be received by a designated person at St George's Hospital Pharmacy, and handled and stored safely and securely in a location only accessible by authorised personnel. Upon receipt, all study IMP will be stored according to instructions specified on the drug labels. Clinical supplies are to be dispensed only in accordance with the protocol. Supplies for patients recruited at the other site(s) will be transferred at ambient temperature and with all required records of dispatch, transfer conditions, and receipt.

The pharmacy will be responsible for maintaining an accurate record of the shipment and dispensing of study IMP in the accountability logs. Patients will be requested to return all unused IMP(s) and packaging at the end of their prescribed study period to the Clinical Trials team. The Clinical Trials team will be responsible for maintaining & updating the drug accountability log with returned IMP, in the hospital pharmacy file.

At the conclusion of the study (or at regular agreed intervals for patient returned IMPs) all study supply accountability records will be cross-checked with remaining study IMP to ensure full accountability before drug destruction.

Drug destruction will be conducted, once agreed by the sponsor and in accordance to local hospital policy, and this will be documented on the drug destruction log in the pharmacy study file.

10.3 Route of administration, dosage, dosage regimen, and treatment period(s) of the IMPs

The study medicine will be taken orally for 28-35 days. The target dosage will be two capsules taken twice daily with meals (metformin 2000 mg/day or placebo). To minimise the risk of gastrointestinal upset, participants will be advised to take the study treatment soon after meals (typically within 20 minutes), and the dose will be escalated as follows:

- Day 1: 500 mg taken after food following first mealtime after randomisation
- Day 2: 500 mg taken after breakfast time and 500 mg after evening mealtime
- Day 3: 1000 mg taken after breakfast time and 500 mg after evening mealtime
- Day 4 until follow-up (day 28–35): 1000 mg taken after breakfast time and 1000 mg after evening mealtime

10.4 Dosage modifications

In the event that a patient suffers mild gastrointestinal side effects (including, but not limited to, diarrhoea, nausea, vomiting, abdominal discomfort, and taste disturbance), headache, or weakness, the drug will be continued provided the side effects are mild and tolerable. If the side effects are not tolerable, treatment with the study drug will either be reduced in dosage (to the last tolerated dosage), or suspended, depending on the severity of the side effect, the degree of discomfort it has caused, and the wishes of the patient.

Following dose-reduction or suspension of the study treatment, one attempt will be made to re-introduce the drug and/or increase it to target dose, after resolution of the side effects. The timing of this will be judged on a case-by-case basis. If on this attempt the drug cannot be tolerated at any dose due to recurrence of side effects, it will be discontinued. If the drug can be tolerated at a sub-maximal dosage, then it will be continued at this lower dosage until study completion.

All decisions on dose modification will be made or confirmed by a medically-qualified member of the study team.

10.5 Assessment of compliance

During the inpatient phase, administration of the study treatment will be supervised and documented by nursing staff. In the event that at the study treatment is not administered, the reason will be recorded in the study folder.

During the outpatient phase, compliance will be assessed by pill counts and by structured interview.

10.6 Post-trial IMP arrangements

The study treatment will be stopped on completion of the treatment period. No provisions have been made to continue the treatment beyond this period, as it is unlikely that this would be clinically indicated. However, if information collected in the study suggested that the patient may have undiagnosed and/or undertreated diabetes mellitus, the patient, and with their

consent, their general practitioner, will be informed of this such that further assessment and treatment may be instituted.

10.7 Name and description of each NIMP

All patients regardless of allocation to metformin or placebo treatment will be prescribed prednisolone 30 mg daily, administered orally, for a minimum of 7 days. This is consistent with current guidelines for the management of patients requiring hospitalisation for COPD exacerbations.⁴ Prednisolone will be routinely prescribed and obtained from normal hospital stocks. There are no special labelling requirements over and above the normal Pharmacy labelling SOP. Any suspected Adverse Drug Reactions or side effects that may be attributable to the administration of prednisolone will be reported through the Yellow Card system.

The McKenzie skin blanch test will be performed using beclometasone diluted in ethanol, administered by topical application. Confirmation that beclometasone used in this context is considered a NIMP has been obtained from the Medicines and Healthcare Products Regulatory Agency Clinical Trials Helpline.

11 Pharmacovigilance

11.1 Definitions

Adverse Event (AE)—any untoward medical occurrence in a patient or clinical trial subject administered an IMP and which does not necessarily have a causal relationship with this treatment (i.e. any unfavourable or unintended change in the structure (signs), function (symptoms), or chemistry (lab data) in a subject to whom an IMP has been administered, including occurrences unrelated to that product).

Adverse Reaction (AR)—any untoward and unintended responses to an IMP related to any dose administered (i.e. any unfavourable or unintended change in the structure (signs), function (symptoms), or chemistry (lab data) in a subject to whom an IMP has been administered and related to any dose administered).

Serious Adverse Event (SAE) or Serious Adverse Reaction (SAR)—any Adverse Event or Reaction in a trial subject that:

- Results in death; or
- Is life-threatening (places the subject in the view of the investigator at immediate risk of death)
- Requires hospitalisation or prolongation of existing hospitalisation (hospitalisation is defined as an inpatient admission, regardless of length of stay; even if it is a precautionary measure for observation; including hospitalisation for an elective procedure, for a pre-existing condition)
- Results in persistent or significant disability or incapacity (substantial disruption of one's ability to conduct normal life functions)

- Consists of a congenital anomaly or birth defect (in offspring of subjects or their parents taking the IMP regardless of time of diagnosis).

Important medical events that may not be immediately life-threatening or result in death or hospitalisation but may jeopardise the subject or may require intervention to prevent one of the outcomes listed in the definition of serious will also be considered serious.

Suspected Unexpected Serious Adverse Reaction (SUSAR)—an Adverse Reaction which is classed in nature as both serious and unexpected.

Unexpected adverse reaction means an adverse reaction the nature and severity of which is not consistent with the information about the medicinal product in question set out in the Summary of Product Characteristics,³⁶ the latest edition of the British National Formulary, and/or in this protocol.

11.2 Recording Adverse Events (AEs)

All Adverse Events will be recorded in the hospital notes in the first instance.

If the Investigator suspects that the disease has progressed faster due to the administration of the IMP, then he will report this as an unexpected adverse event to the Sponsor.

Clinically significant abnormalities in the results of objective tests (*e.g.* laboratory variables) may also be recorded as Adverse Events.

Metformin has been in common use for over 50 years. Considerable experience has been amassed regarding its risk profile in diabetes mellitus, polycystic ovary syndrome, and in a wide range of co-incidental diseases. These data have been gathered both from clinical practice and more than 70,000 patient-years of exposure within clinical trials.⁴¹ Although this study concerns the use of metformin outside of its licensed indication, and which has not previously been studied in the clinical trial setting, it is not novel in clinical practice. An audit conducted in this hospital indicated that approximately one-third of patients hospitalised with COPD and diabetes mellitus are treated with metformin, and it is continued after admission in approximately three-quarters of these. We feel that this practice is likely to be representative of practice elsewhere. As such, our assessment is that the safety profile of metformin in this context is well-characterised. Intensive recording and notification of all Adverse Events is extremely unlikely to reveal any previously unrecognised adverse reactions.

11.3 Procedures for recording and reporting SAEs

The following descriptions will be used to record AEs:

Clinical symptoms—a simple and brief description.

Severity will be described using following categories:

- **Mild**—the adverse event does not interfere with the volunteer's daily routine, and does not require intervention; it causes slight discomfort.

- **Moderate**—the adverse event interferes with some aspects of the volunteer’s routine, or requires intervention, but is not damaging to health; it causes moderate discomfort.
- **Severe**—the adverse event results in alteration, discomfort or disability which is clearly damaging to health.

Relationship to treatment—the assessment of relationship of AEs to the administration of IMP is a clinical decision based on all available information at the time of the completion of the CRF. The following categories will be used:

- **Definitely**—there is clear evidence to suggest a causal relationship, and other possible contributing factors can be ruled out.
- **Probably**—there is evidence to suggest a causal relationship, and the influence of other factors is unlikely.
- **Possibly**—there is some evidence to suggest a causal relationship (e.g. the event occurred within a reasonable time after administration of the trial medication). However, the influence of other factors may have contributed to the event (i.e. the patient’s clinical condition, other concomitant events).
- **Unlikely**—there is little evidence to suggest there is a causal relationship (e.g. the event did not occur within a reasonable time after administration of the trial medication). There is another reasonable explanation for the event (e.g. the patient’s clinical condition, other concomitant treatments).
- **Not related**—there is no evidence of any causal relationship.
- Not Assessable

Expectedness, where applicable, will be assessed for Adverse Reactions according to the following definitions:

- **Expected**—an Adverse Reaction that is consistent with the information about the IMP listed in the SmPC.
- **Unexpected**—an Adverse Reaction that is not consistent with the information about the IMP listed in the SmPC.

Collection, recording and reporting of AEs (including serious and non-serious events and reactions) to the Sponsor will be done according to Sponsor’s Pharmacovigilance SOP.

All SAEs will be recorded in the hospital notes and the CRF, and the sponsor’s SAE Recording Log. The SAE Log will be sent to Sponsor on request and every 2 months.

All SAEs will be reported to the Sponsor via the JRO on an SAE form unless stated in the protocol that some expected SAEs will not be reported to the Sponsor, with justification as to why they will not be reported.

The Chief or Principal Investigator will complete the Sponsor’s SAE form and the form will be faxed to the JRO on [name] or e-mailed to [contact], within 24hrs of his/her becoming aware of the event.

The Chief or Principal Investigator will respond to any SAE queries raised by the Sponsor as soon as possible.

All SUSARs will be notified to the Sponsor immediately or at least within 24hrs of the Investigator becoming aware of the event.

11.4 Protocol Defined Events (PDEs)

This trial involves patients hospitalised for exacerbations of COPD, a condition that is associated with high morbidity and mortality. The in-hospital mortality rate has been reported to range between 4% and 30%. In an audit of a subset of patients with COPD (those who also had diabetes mellitus), 14/108 (13%) required non-invasive ventilation for respiratory failure, and 17/108 (16%) died in-hospital or within 30 days of discharge.

Many important and potentially Serious Adverse Events (SAEs) are common in the population under study, which are unlikely to be related to the IMP, but rather the underlying disease or co-morbidities and these will be identified and reported as Protocol Defined Events. A list of anticipated PDEs is presented below. The occurrence of any of the events listed below will be documented in the patients hospital notes, CRFs and Sponsor's AE Log. The PDEs will not be reported to Sponsor immediately using the SAE Reporting Form. However, the Sponsor will be made aware on regular review of the completed AE Log through submission to the JRO on request or every 2 months. Similarly, an assessment of expectedness will not be required unless they fall within the definition of an Adverse Reaction.

- Failure to recover to baseline
- Recurrent exacerbation of COPD
- Pneumonia
- Respiratory failure
- Sepsis

For the avoidance of doubt, a Protocol Defined Event remains as such even if it has an attribute that defines it at a Serious Adverse Event (for example, a recurrent exacerbation of COPD requiring hospital admission should be treated as a Protocol Defined Event).

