In this study, we consider there to be a risk of lactic acidosis related to the underlying condition (COPD) and commonly associated comorbidities (such as respiratory failure, heart failure, renal failure and severe sepsis). As noted above, the lactate levels and prognosis observed in cases of lactic acidosis are believed to be dictated by with the severity of the underlying condition, rather than to the presence or plasma concentration of metformin.^{40,68} Nevertheless, given the lack of certainty over the safety of metformin therapy in such settings, and to avoid potential confusion over the aetiological agent, we shall stop or suspend the study drug if a condition develops in which there is a high risk of lactic acidosis, or if the plasma lactate concentration rises above pre-specified levels.

Further, we consider that there is a small but genuine risk of metformin-associated lactic acidosis if metformin is allowed to accumulate due to renal failure. To mitigate this, we will monitor the renal function regularly while the participant is an inpatient (when, due to the severity of their concurrent illnesses, the risk of developing renal failure is greatest), and stop or suspend the study treatment if the estimated GFR falls, or the serum creatinine rises, above pre-specified levels.

We judge that the risk of metformin-associated lactic acidosis outside the situations described above is extremely low. This risk must be balanced against the seriousness of the condition under study. As noted above, the 90-day mortality rate following hospitalisation for a COPD exacerbation is 13.9%; the 5-year mortality rate exceeds 50%. Observational data suggest that

lowering blood glucose concentration may offer the prospect of substantial benefit. As such, our assessment is that the risk–benefit balance lies in favour of undertaking this trial.

5 Study objectives

The overarching research question for this body of work is to ascertain whether metformin improves recovery from COPD exacerbations. This pilot study will address two more limited questions, as a basis for future trial design.

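### Section 11.4 exempts five event types from immediate SAE reporting by name, does not exclude cases judged drug-related, and is not reconciled with section 11.3

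*Protocol*

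**What the plan says.** Protocol section 11.4 defines a class of Protocol Defined Events (PDEs) with five members: failure to recover to baseline, recurrent COPD exacerbation, pneumonia, respiratory failure and sepsis. The reason for the class is that these are common events "which are unlikely to be related to the IMP, but rather the underlying disease or co-morbidities". Four provisions follow.

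- Timing: "The PDEs will not be reported to Sponsor immediately using the SAE Reporting Form". The sponsor learns of them from the AE Log, through "submission to the JRO on request or every 2 months".
- Seriousness: "a Protocol Defined Event remains as such even if it has an attribute that defines it at a Serious Adverse Event".
- Relatedness, mentioned once and only for expectedness: "an assessment of expectedness will not be required unless they fall within the definition of an Adverse Reaction".
- Precedence over, or deference to, section 11.3: nothing is said.

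Section 11.3 sends all SAEs to the sponsor on the SAE form within 24 hours, "unless stated in the protocol that some expected SAEs will not be reported to the Sponsor", and asks for a justification of any such exemption. It then says: "All SUSARs will be notified to the Sponsor immediately or at least within 24hrs of the Investigator becoming aware of the event". That sentence contains no exclusion for PDEs. Section 11.5 requires every death to be reported within 24 hours, whatever its cause.

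**The concern.** The exemption is attached to the name of the event, while its justification concerns causation. Once an investigator has judged a particular case of sepsis or respiratory failure to be possibly, probably or definitely related to study drug, the justification no longer applies to that case. The exemption, as worded, still does.

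The drafters had related cases in mind, because they restored the expectedness assessment for PDEs that are Adverse Reactions. They did not carry the same condition into the timing sentence. A site that reads 11.4 alone would log such a case and send no form.

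This matters for the risk the protocol treats most seriously. Section 4.6.3 names respiratory failure and severe sepsis among the comorbidities that carry a risk of lactic acidosis. The definition of severe sepsis in section 7.2 counts a lactate above 2 mmol/L as a sign of tissue hypoperfusion. A lactate problem related to study drug could therefore be recorded under a PDE label. Section 14.6 plans no interim analysis and ends the trial on one case of lactic acidosis on active drug judged definitely or probably related. That rule depends on related events reaching the sponsor promptly.

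**Working it through.** No sample size, power or error rate is involved. The check traces each kind of serious listed event through sections 11.1 and 11.3 to 11.6.

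**Step 1. Definitions.** Under 11.1 an event related to the drug is an Adverse Reaction, and an Adverse Reaction that is serious and unexpected is a SUSAR. A serious reaction that is expected is therefore not a SUSAR.

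**Step 2. Routing.**

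| Serious listed event | Text that governs | Time to sponsor |
|---|---|---|
| Fatal, any relationship | 11.5 | 24 hours |
| Non-fatal, judged unlikely or not related | 11.4 | Log, up to 2 months (the intended use) |
| Non-fatal, related, unexpected (SUSAR) | 11.3 says 24 hours; 11.4 says no immediate form | 24 hours under 11.3, with a conflicting instruction in 11.4 |
| Non-fatal, related, expected | 11.3 permits an exemption for some expected SAEs; 11.4 uses it | Log, up to 2 months, no breach |

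**Step 3. The third row.** A SUSAR left in the log would breach 11.3, so 11.3 governs on any careful reading. But 11.6 sends SUSARs to the JRO with the SAE form. It starts the 7-day clock for fatal or life-threatening cases when that form is received and dated, and 11.4 says this form is not sent immediately. The two instructions collide and no order of precedence is given.

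**Step 4. The fourth row.** Whether a related listed event counts as expected depends on the section consulted. Section 11.1 compares it with the SmPC, the British National Formulary and/or this protocol. Section 11.3 compares it with the SmPC alone. Since 11.4 lists these events as anticipated, an investigator using 11.1 could class one as expected because the protocol names it. Using 11.3, the same event would be unexpected unless the SmPC lists it. The first reading puts it in row four, the second in row three.

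**Step 5. The authority for the exemption.** Section 11.3 allows exemption only for some expected SAEs. Section 11.4 waives the expectedness assessment for PDEs that are not Adverse Reactions, and its timing sentence is not confined to expected events. The exemption as written is wider than the clause that permits it.

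**Step 6. Size of the delay.** Two months is 2 × 365.25 / 12 = 60.9, about 61 days, against 1 day. This is an outer limit, because the log may also be called for at any time.

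**The case against.** A reader might infer from 11.4 that the protocol lets a SUSAR wait two months. The documents do not support that. Section 11.3 covers all SUSARs within 24 hours, 11.6 routes them with the SAE form, and 11.4 nowhere cancels either. The expectedness clause in 11.4 leads into the SUSAR rule: a related PDE is assessed, and if serious and unexpected it falls under 11.3. The seriousness clause refers to a Serious Adverse Event, not to a reaction or a SUSAR, and its example is a readmission for exacerbation. All of this stands.

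It can also be said that lactic acidosis, raised lactate and metabolic acidosis are not on the PDE list. When serious, they go on the SAE form in the usual way. Protection of the individual patient does not wait for the log, because section 9.10.2 acts on lactate, severe sepsis, metabolic acidosis and decompensated respiratory failure as they occur. This also stands, and it limits the consequence to sponsor oversight.

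A reader might try to size the problem from the audit in 11.4, in which 14 of 108 patients needed non-invasive ventilation. That rate does not measure it. Those patients had diabetes, the trial excludes decompensated respiratory failure at entry, and the affected events are only those that are serious, non-fatal, judged related and classed as expected. The documents give no rate for these.

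Finally, 11.4 lists these events as features of the disease, whereas 11.1 refers to information about the product. An investigator need not treat the list as making a reaction expected. That is a fair reading, but nothing in the text requires it. Section 11.3 also defers to the sponsor's pharmacovigilance SOP, which is not shown and might deal with related PDEs. If so, 11.4 should say so.

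**Conclusion.** The point holds as an unreconciled conflict between 11.3 and 11.4, together with one real gap.

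- The conflict: the exemption rests on presumed unrelatedness but is applied by event name, and nothing says that SUSAR reporting under 11.3 prevails. A SUSAR kept in the log would be a site error that the wording invites, not something the protocol allows.
- The gap: a serious, related, non-fatal PDE classed as expected can wait up to about 61 days in the log without any breach.

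The gap rests on two assumptions: that an investigator classes the event as expected, which 11.1 permits more readily than 11.3, and that the sponsor does not call for the log earlier. The number of such events cannot be estimated from the protocol. Sample size, power and type I error are unaffected. This is a cheap and worthwhile correction to safety reporting, not a defect that undermines the trial.

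**What to change.** In section 11.4:

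1. State that the exemption applies only to events the investigator has assessed as *Unlikely* or *Not related*.
2. State that any serious PDE judged possibly, probably or definitely related is reported on the SAE form within 24 hours under 11.3.
3. State that SUSAR reporting under 11.3 takes precedence over 11.4.
4. Require relatedness to be recorded when each PDE is entered in the log.

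In sections 11.1 and 11.3, use one and the same reference for expectedness.

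Section 11.3 also has a *Not Assessable* category. Under item 1 it would fall outside the exemption and return to the ordinary SAE rule. If the sponsor wants otherwise, the text should say so.

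The cost is a few sentences, one column in the AE Log and a few extra SAE forms. Events judged unrelated keep the lighter route that 11.4 was written to provide.
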